## PROTOCOL SYNOPSIS

### Title:

Phase I/IIa study of oral 5-azacitidine in combination with the histone deacetylase inhibitor romidepsin for the treatment of patients with T-cell lymphomas

### Study Design:

This is an open label, phase I/IIa, 3 x 3 dose-escalation study with an initial phase I followed by a disease focused phase II.

The primary objective of the phase I is to determine the maximum tolerated dose (MTD) and dose limiting toxicity (DLT) of the combinations of oral 5-azacitidine and romidepsin in patients with lymphoma. The safety and toxicity of this combination will be evaluated throughout the entire study.

If the combination of oral 5-azacitidine and romidepsin is found to be feasible and an MTD is established, the phase II part of the study will be initiated.

Phase II will consist of a 2 stage design of the combination of oral 5-Azacitidine and romidepsin for patients with relapsed or refractory T-cell lymphomas.

### Objectives:

#### A. Phase I:

##### **Primary Objectives**

- Determine the maximum tolerated dose (MTD) and dose limiting toxicity (DLT) of the combination of oral 5-azacitidine and romidepsin.
- Evaluate the safety and toxicity of the combination of oral 5-azacitidine and romidepsin.

##### **Secondary Objectives**

- Describe the maximum number of cycles received
- Describe the number of dose delays and dose reductions at the MTD
- Describe the anti-tumor activity of the combination
- Evaluate the overall response rate (ORR), progression free survival (PFS), and duration of response (DOR) of the study population.

##### **Exploratory Objectives**

- Evaluate pharmacodynamic markers of drug effect in paired tissue biopsies (pre- and post- treatment) including gene expression and genome wide methylation patterns.
- Establish the pharmacokinetic profile for oral 5-azacitidine and romidepsin when given as a combination in Cycle 1 at various time intervals as listed in Figure 1.

B. Phase II:

**Primary Objectives**

- Estimate the ORR (complete + partial response) of the combination of oral 5-azacitidine and romidepsin in patients with relapsed/refractory T-cell Lymphoma.

**Secondary Objectives**

- Estimate the DOR and PFS of the combination in patients with T-cell lymphoma.
- Estimate the overall survival of patients with T-cell lymphoma on study.
- Identify potential pre-treatment biomarkers of response based on GEP and/or methylation array to clinical outcome.

**Exploratory Objectives**

- Evaluate pharmacodynamic markers of drug effect in paired tissue biopsies (pre- and post- treatment) including gene expression and genome wide methylation patterns.

C. Exploratory Cohort: Germinal Center B-cell Lymphoma:

**Primary Objectives**

- Determine the overall response rates (complete responses + partial responses) of oral azacytidine and romidepsin in patients with GC-derived B-cell lymphomas.
- Determine Progression Free Survival (PFS) and Time to Treatment Failure (TTF)
- Determine the Duration of Response (DOR)

**Secondary Objectives:**

- Determine the safety and tolerability of oral azacytidine and romidepsin in patients with relapsed or refractory GC-derived B-cell lymphoid malignancies.
- Evaluate the pharmacokinetic (PK) profile of oral azacytidine and romidepsin.
- Evaluate and compare pharmacodynamic (PD) endpoints with PK endpoints. PD endpoints will include the evaluation of paired gene expression profiles of primary patient samples on study.

**Target Population**

**Phase I:** Patients with relapsed or refractory non-Hodgkin lymphoma, Hodgkin lymphoma

**Phase II:** Patients with untreated or relapsed or refractory T-Cell Lymphoma

**Exploratory Cohort:** Patients with relapsed or refractory Germinal Center-Derived B-Cell Lymphoma

**Inclusion Criteria**

- **Phase I:** Patients must have histologically confirmed relapsed or refractory non-

Hodgkin lymphoma or Hodgkin lymphoma (defined by WHO criteria), with no accepted curative options.

**Phase II:** Patients must have histologically confirmed T-cell lymphoma (as defined by WHO criteria), including central nervous system (CNS) involvement or lymphomatous meningitis.

**Exploratory Cohort:** Patients with histologically confirmed relapsed or refractory Germinal Center (GC)-derived B-Cell Lymphoma (diffuse large B-cell (DLBCL) and follicular lymphoma (FL)) defined by the WHO and Hans criteria with no accepted curative options. (Appendix 5)

- There is no upper limit for the number of prior therapies
- Evaluable Disease in the Phase I, and measurable disease as defined in Section 11.1 in the Phase II.
- Age  $\geq 18$  years.
- ECOG performance status  $\leq 2$
- Patients must have adequate organ and marrow function as defined in Section 3.1.6
- Adequate Contraception
- Ability to understand and the willingness to sign a written informed consent document.

## Exclusion Criteria

- Prior Therapy
  - Exposure to chemotherapy or radiotherapy within 2 weeks prior to entering the study or those who have not recovered from adverse events due to agents administered more than 2 weeks earlier.
  - Systemic steroids that have not been stabilized ( $\geq 5$  days) to the equivalent of  $\leq 10$  mg/day prednisone prior to the start of the study drugs.
  - No other investigational agents are allowed.
- History of allergic reactions to oral 5-azacitidine or romidepsin.
- Uncontrolled inter-current illness
- Pregnant women
- Nursing women
- Current malignancy or history of a prior malignancy, as outlined in Section 3.3.7
- Patient known to be Human Immunodeficiency Virus (HIV)-positive
- Active Hepatitis A, Hepatitis B, or Hepatitis C infection

## Treatment Plan (Phase I)

Patients will be treated with oral 5-azacitidine and romidepsin administered as follows (detailed in Table 2): escalating oral 5-azacitidine from Days 1-14 (Dose cohorts -1 to 5) or Days 1-21 (Dose Cohort 6); and romidepsin administered intravenously on Days 8, 15 (Dose cohorts 1-4) of a 28 day cycle and Day 22 (Dose Cohorts 5 and 6) of a 35 day cycle. Cohorts of 3 patients will be enrolled sequentially as outlined in the dose escalation scheme

(Table 2). Once the MTD is reached the Phase II part of the protocol will be initiated in patients with T-Cell Lymphoma (Figure 2).

#### **Treatment Plan (Phase II and Exploratory Cohort)**

Patients will be treated with oral 5-azacytidine and romidepsin at the MTD (i.e the Recommended Phase 2 Dose, or RP2D). The treatment will be administered as follows: oral 5-azacytidine 300 mg (flat dose) Days 1-14 and romidepsin 14 mg/m^2 on Days 8, 15, and 22 on an every 35 day cycle. .

#### **Duration of Treatment**

Patients will be treated until one of the following events:

- Disease progression
- Unacceptable adverse event(s), DLTs
- Withdrawal of consent
- General or specific changes in the patient's condition that render the patient unacceptable for further treatment in the judgment of the investigator
- An event that in the judgment of the treating physician warrant's discontinuation of therapy.

#### **Sample Size**

##### Phase I

An estimated 36 patients (max of 45) will be accrued to the initial Phase I study; a minimum of 3 patients will be treated at each of the 6 dose levels (Dose Escalation and de-escalation; Tables 3 & 4). If a DLT is reached early we will treat fewer patients. We will expand the cohort which meets criteria for a DLT to a total of 6.

##### Phase II

The phase II part of the study will accrue a total of 24 patients.

##### Exploratory Cohort

The exploratory cohort part of the study will accrue a total of 10 patients.

#### **Safety**

Patients will be monitored carefully for the development of adverse events as well as clinical and/or radiographic evidence of disease response. Adverse events will be evaluated according to criteria outlined in the NCI Common Terminology Criteria for Adverse Events (CTCAE), version 4.0.

[figure not shown]
#### **Efficacy Outcome**

Overall response rates will be evaluated using clinical parameters, CT scan (PET/CT scan is optional) and bone marrow biopsy, as outlined by the 2007 International Harmonization Project criteria.[1]

#### **Pharmacokinetic Analyses ( T-Cell Population ONLY)**

[figure not shown]
- Pharmacokinetic studies will be performed on up to 10 patients in the Phase 2. A pre-treatment blood sample will be obtained prior to starting 5-azacytidine and romidepsin. On day 8 of cycle 1, blood samples will be obtained from patient's at fixed time intervals after administration of Romidepsin ( $t_{1/2} = 3.5$  hours) to determine the plasma level of both romidepsin and oral 5-azacytidine. The patient will be directed to take 5-azacytidine at the time the romidepsin infusion begins. This will be compared to the known pharmacokinetic data for the individual agents in order to identify any possible effect of the combination. The proposed time points are shown in Figure 1.

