**Figure 1: Drug Administration and Pharmacokinetic Sampling Schedule (Day 1)**

[figure not shown]

\* All PKs should be drawn within 15 minutes of specified time.

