### **2.2.3 Clinical Pharmacokinetics**

The pharmacokinetics of azacitidine were studied in 6 MDS patients following a single 75 mg/m^2 subcutaneous (SC) dose and a single 75 mg/m^2 intravenous (IV) dose. Azacitidine is rapidly absorbed after SC administration; the peak plasma azacitidine concentration of  $750 \pm 403$  ng/ml occurred in 0.5 hour. The bioavailability of SC azacitidine relative to IV azacitidine is approximately 89%, based on area under the curve. Mean volume of distribution following IV dosing is  $76 \pm 26$  L. Mean apparent SC clearance is  $167 \pm 49$  L/hour and mean half-life after SC administration is  $41 \pm 8$  minutes.

Published studies indicate that urinary excretion is the primary route of elimination of azacitidine and its metabolites. Following IV administration of radioactive azacitidine to 5 cancer patients, the cumulative urinary excretion was 85% of the radioactive dose. Fecal excretion accounted for <1% of administered radioactivity over 3 days. Mean excretion of radioactivity in urine following SC administration of C-azacitidine was 50%. The mean elimination half-lives of total radioactivity (azacitidine and its metabolites) were similar after IV and SC administrations, about 4 hours.

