#### 5.1.4

#### Guidelines for Study Drug Administration

- Oral 5-azacitidine will be taken between the hours of 8 and 10 am daily (patient will be required to maintain a drug log recording side effects and time of dosage) on Days 1-14
- Romidepsin will be administered over 4 hours through either a peripheral or central venous catheter on Days 8, 15, 22 of a 35 day cycle. It will be administered within 6 hours of the oral dose. On the day of PK sampling in Cycle 1, the azacitidine will be taken with romidepsin. A dose of the anti-emetic will be administered in accordance with the package insert of romidepsin.
- Administration of the study drugs will be allowed within 48 hours of the scheduled dates.
- Missed doses will not be made up.

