d) PK for Oral 5-azacitidine /Romidepsin: See figure 1 for details.  
e) To be done within 4 weeks of treatment start date  
f) To be done within 1 week of treatment start date  
g) Not necessary if conducted within 72 hours of screening assessment  
h) PD for Oral 5-azacitidine /Romidepsin: See figure 1 for details.  
i) Sodium, potassium, chloride, calcium, and glucose are part of the electrolyte assessment at every time point. Magnesium and phosphorous will be added to the electrolyte panel at Screening, and repeated before administration of romidepsin.  
j) Follow-up visits will be every 3 months for 1 year, or until the patient begins a new treatment for their disease for any patient that did not progressed on study.  
k) Based on clinical assessment  
l) For CNS disease only. Follow up MRI to be done at the discretion of the treating investigator.

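### The interaction question rests on a cross-study comparison alone; for azacitidine, a within-patient Day 8/Day 1 ratio should be added if Figure 1 holds post-dose Day 1 samples

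*Combined protocol and SAP*

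**What the plan says.** The synopsis section on pharmacokinetic analyses states: "Pharmacokinetic studies will be performed on up to 10 patients in the Phase 2". Before treatment there is one draw: "A pre-treatment blood sample will be obtained prior to starting 5-azacytidine and romidepsin". On Day 8 of Cycle 1, blood is taken at fixed intervals for both drugs, with azacitidine swallowed as the romidepsin infusion starts. The analysis is then one sentence: "This will be compared to the known pharmacokinetic data for the individual agents in order to identify any possible effect of the combination". Section 9.1 only points to Figure 1, Section 13 contains no PK analysis, and no within-patient comparison appears anywhere.

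The places that bear on Day 1 do not quite agree:

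- Figure 1 is captioned as a Day 1 sampling schedule and carries the note "All PKs should be drawn within 15 minutes of specified time". A separate Figure 1a is captioned for Day 8.
- The Section 10 calendar marks PK on Cycle 1 Day 1 and Day 8, both with footnote d: "PK for Oral 5-azacitidine /Romidepsin: See figure 1 for details". One further mark, without a footnote, appears to fall on Cycle 2 Day 1.
- Section 5.1.4 reads as if Cycle 1 had one PK day: "On the day of PK sampling in Cycle 1, the azacitidine will be taken with romidepsin".

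On reference data, Section 2.2.3 says: "The pharmacokinetics of azacitidine were studied in 6 MDS patients following a single" 75 mg/m² subcutaneous dose, and likewise after an intravenous dose of the same size. Section 2.3.5 gives romidepsin values at 14 mg/m² in T-cell lymphoma: Cmax 377 ng/mL and AUC 1549 ng·hr/mL. Section 1.6 lists PK as an exploratory Phase II objective.

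**The concern.** A comparison with outside data mixes any effect of romidepsin with every other difference between the studies. For azacitidine, measured against the data the protocol prints, these are route (oral against subcutaneous or intravenous), formulation, dose (300 mg flat against 75 mg/m²) and disease (T-cell lymphoma against MDS). A difference could be read as an interaction when it reflects the oral route. Agreement could equally hide an interaction that the other differences offset.

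The schedule offers a better reference for this drug. Azacitidine starts on Day 1 and romidepsin on Day 8 (Section 5.1.2), so any post-dose Day 1 sample shows azacitidine without romidepsin in the same patient, at the same dose and in the same formulation. If those samples are drawn and then not used for this purpose, the more informative contrast is left out of the plan.

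**Working it through.** **No figure to reproduce.** The plan gives up to 10 PK patients with no CV, margin, power or interval width behind that number. What follows illustrates precision.

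**Inputs.**
- n = 10 (synopsis).
- Reference n = 6 and between-patient CVs from Section 2.2.3: subcutaneous Cmax 403/750 = 54%; subcutaneous clearance 49/167 = 29%. Clearance is the one relevant to AUC.
- Within-patient CV of azacitidine exposure: not in the documents; assumed 20% to 50%.
- 90% two-sided intervals: assumed.

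**Formulas (log scale).** SD = √ln(1 + CV²). Each interval is the estimated ratio multiplied and divided by exp(t × SE).
- Paired Day 8/Day 1: SE = SD_within × √(2/10), t = 1.833 on 9 df.
- External, 10 against 6 patients: SE = SD_between × √(1/10 + 1/6), t = 1.761 on 14 df.
- External, reference treated as a fixed value: SE = SD_between/√10, t = 1.833 on 9 df.

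**Worked examples.**
- Paired, CV 30%: SD = √ln(1.09) = 0.294; SE = 0.294 × 0.447 = 0.131; exp(1.833 × 0.131) = 1.27.
- External, CV 54%: SD = 0.506; SE = 0.506 × 0.516 = 0.261; exp(1.761 × 0.261) = 1.58.

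| Comparison | CV | 90% CI factor | Ratio detectable (80% power, two-sided 5%; assumed levels) |
|---|---|---|---|
| Paired, n = 10 | 20% | 1.18 | 1.32 |
| Paired, n = 10 | 30% | 1.27 | 1.51 |
| Paired, n = 10 | 40% | 1.37 | 1.72 |
| Paired, n = 10 | 50% | 1.47 | 1.95 |
| External, 10 against 6 | 29% | 1.29 | 1.56 |
| External, 10 against 6 | 54% | 1.58 | 2.20 |
| External, fixed reference | 29% | 1.18 | 1.33 |
| External, fixed reference | 54% | 1.34 | 1.66 |

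The ranges overlap, so pairing does not always give the narrower interval. The external factors, however, contain no allowance for cross-study bias. The documents give no oral PK from which that bias could be sized.

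**Carry-over.** At the 41-minute subcutaneous half-life, 24 hours is 1440/41 = 35 half-lives, leaving about 3 × 10⁻¹¹ of a dose. Residual drug from earlier daily doses should not disturb the Day 8 profile. No oral half-life is given.

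**Romidepsin.** Its first dose is on Day 8, during azacitidine dosing (Days 1–14). Neither Cycle 1 PK day therefore provides a romidepsin profile without azacitidine, and no paired figure can be formed for that drug.

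**The case against.** The strongest reply is that the key samples are not confirmed. A ratio of AUC and Cmax needs serial post-dose draws on Day 1. The synopsis text mentions only a pre-treatment draw, Section 5.1.4 speaks of one PK day, and a single pre-dose sample would also earn the calendar mark. The Figure 1 caption and its timed-draw note make serial Day 1 samples likely, but the time points are in the figure itself, which the public text does not reproduce. This stands, and it makes the recommendation conditional.

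A reader might infer that the planned azacitidine reference is the 6-patient study. The synopsis does not name its reference, and Section 2.2.4 mentions 185 patients given oral azacitidine in company-sponsored studies, without saying whether PK was measured. An oral reference would remove the route difference but leave a cross-study comparison.

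A reader might also infer that pairing isolates the effect of romidepsin. It does not do so fully. The order is fixed, and Day 8 follows seven days of azacitidine and comes with premedication, including the intravenous ondansetron that Section 5.1.7 calls for before romidepsin. These are narrower ambiguities than a change of route, dose and disease, but they remain.

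Finally, it would be wrong to say that romidepsin is never given without azacitidine. Its Day 15 and Day 22 doses fall after azacitidine ends on Day 14; PK is simply not scheduled then.

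**Conclusion.** The point holds for azacitidine and is conditional on post-dose Day 1 samples. As written, the plan looks for a combination effect only across studies, and the azacitidine data printed in the protocol differ in route, dose and disease. A within-patient Day 8/Day 1 ratio removes those sources of bias.

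The documents do not support a claim that it is always more precise: 1.18 to 1.47 for the paired ratio, against 1.29 to 1.58 or 1.18 to 1.34 for the external comparison, depending on how the reference is treated. The paired range rests on an assumed within-patient CV. Under the same assumptions, 10 patients would reliably detect only ratios of about 1.3 to 2, so a null result should not be reported as absence of interaction.

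For romidepsin the external comparison has to stay. The aim is exploratory and no sample size, error rate or response conclusion depends on it, so priority is low.

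**What to change.** Add to the synopsis PK section and to Section 13 wording such as:

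> For azacitidine, the effect of romidepsin will be described by the within-patient ratio Day 8 / Day 1 of Cycle 1 for AUC and Cmax. Geometric mean ratios with 90% confidence intervals will be obtained from a paired analysis of log values in patients with evaluable profiles on both days. Comparison of romidepsin with published single-agent values is descriptive.

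State alongside it that the ratio may also reflect repeated azacitidine dosing and Day 8 premedication. Any comparison of azacitidine with outside data should name its source and be labelled descriptive.

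Reconcile the synopsis text, the Figure 1 caption and note, Section 5.1.4 and the Section 10 calendar on what is drawn on Day 1, and say what the apparent Cycle 2 Day 1 mark is for.

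If Figure 1 already has post-dose Day 1 times matching Day 8, the cost is analysis wording. If not, a few added Day 1 draws are needed in up to 10 patients. Fewer complete pairs would cost precision: with 6, the 90% CI factor is 1.26 to 1.73 over the same assumed CV range.

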**Figure 1: Drug Administration and Pharmacokinetic Sampling Schedule (Day 1)**

[figure not shown]

\* All PKs should be drawn within 15 minutes of specified time.

**Figure 1a: Drug Administration and Pharmacokinetic Sampling Schedule (Day 8)**

**Figure 1b: Drug Administration and Pharmacodynamic Sampling Schedule**

**SCHEMA**

**Table 1: Regimen Description**

REGIMENT DESCRIPTION					
Agent	Premedications; Precautions	Dose	Route	Schedule	Cycle Length
Oral 5-azacitidine	Standard Premedications	300 mg (flat dose)	PO Days 1-14	Days 1-14	35 days
Romidepsin	Antiemetic	14 mg/m 	IV over 4 hours	Days 8, 15 and 22	
** Doses as appropriate for assigned dose level.					

**Table 2: Dose Escalation Scheme for the Combination of Oral 5-azacitidine and Romidepsin**

Dose Escalation Schedule			
Dose Level	Dose		Cycle Length
	Oral 5-azacitidine (Flat dose [mg])	Romidepsin (mg/m  rounded to 14mg/m  )	
Level -1	100 (Days 1-14)	10 (Day 8)	28
Level 1	100 (Days 1-14)	10 (Days 8 & 15)	28

Level 2	200 (Days 1-14)	10 (Days 8 & 15)	28
Level 3	300 (Days 1-14)	10 (Days 8 & 15)	28
Level 4	300 (Days 1-14)	14 (Days 8 & 15)	28
Level 5	300 (days 1-14)	14 (Days 8, 15 and 22)	35
Level 6	300 Days (1-21)	14 (Days 8, 15, 22)	35

**Figure 2: Drug Administration Schema**

**Dose Levels -1 through 4**

Day	1	8	15	21	28
Oral 5-azacitidine	↓	↓	↓	↓	↓
Romidepsin			↓		↓

**Dose Level 5**

Day	1	8	15	21	28	35
Oral 5-azacitidine	↓	↓	↓	↓	↓	↓
Romidepsin			↓		↓	↓

**Dose Level 6**

Day	1	8	15	21	28	35
Oral 5-azacitidine	↓	↓	↓	↓	↓	↓
Romidepsin			↓		↓	↓

[figure not shown]
**Table 3: Dose Escalation & De-Escalation Decision Rules:**

Number of Patients with DLT at a Given Dose Level	Escalation Decision Rule
0 out of 3	Enter 3 patients at the next dose level.
1 out of 3	
Enter at least 3 more patients at this dose level.
 
 
If 0 of these 3 additional patients experience DLT, proceed to the next dose level.
 
If 1 or more of this group experience DLT, then dose escalation is stopped, and this dose is declared the maximally administered dose (MAD), and the dose level below is the MTD.
 

$\geq 2$	Dose escalation will be stopped. This dose level will be declared the maximally administered dose (highest dose administered).
$\leq 1$ out of 6 at highest dose level below the maximally administered dose	This is generally the recommended phase 2 dose. At least 6 patients must be entered at the recommended phase 2 dose.

**Figure 3: Study Plan Flow Chart**

Schema: Phase 1

## A. Schema Phase II and Exploratory Cohort

- Oral 5-azacitidine and romidepsin administered at the MTD of the combination to patients with T-Cell Lymphoma: oral 5-azacytidine at 300 mg (flat dose) Days 1-14 and romidepsin 14 mg/m^2 on Days 8, 15 and 22 on a 35 day cycle.
- For Exploratory Cohort Only: Lymph node biopsy for determination of gene expression profile

### CYCLE 1

#### Intervention

Drugs are administered as outlined above

#### Evaluations

Safety evaluations on Days 1, 8, 15 and 22.

Laboratory Evaluations Days 1, 8, 5 and 22

For Exploratory Cohort Only:

Optional lymph node biopsy on day 8 -21

### Future Cycles

#### Intervention

Both drugs given at the MTD

#### Tests

Safety evaluations on Day 1

Laboratory Evaluations Days 1, and each day of romidepsin

CT scans at the end of cycles 2 and 6. Then CT scans q3-6 months, until disease progression or initiation of new therapy.  
(PET/CT is optional)

